7.1.1.1 Intensity

All clinical AEs encountered during the clinical study will be reported on the AE eform of the eCRF. Intensity of AEs will be graded on a three-point scale [mild, moderate, severe] and reported in detail on the eCRF.

Mild	discomfort noticed but no disruption of normal daily activity.
Moderate	discomfort sufficient to reduce or affect daily activity.
Severe	inability to work or perform normal daily activity

7.1.1.2 Drug - Adverse event relationship

The relationship of the AE to the treatment should always be assessed by the investigator.

The relationship can be one of two possibilities:

- No (unrelated; equals not drug related).
- Yes (the event has a reasonable suspected causal relationship to the drug, or causality is unknown).

The criteria used for determining causality relationship can be found in [Appendix 1](#).

7.1.1.3 Serious Adverse Events [Immediately Reportable to Roche]

A Serious Adverse Event (SAE) is any experience that suggests a significant hazard, contraindication, side effect or precaution. It is any AE that at any dose fulfills at least one of the following criteria:

- is fatal; [results in death**; NOTE: death is an outcome, not an event]
- is life threatening [NOTE: the term "life-threatening" refers to an event in which the subject was at immediate risk of death at the time of the event; it does not refer to an event which could hypothetically have caused a death had it been more severe].
- requires in-patient hospitalization or prolongation of existing hospitalization;
- results in persistent or significant disability/incapacity;
- is a congenital anomaly/birth defect;

- is medically significant or requires intervention to prevent one or other of the outcomes listed above.

**The term sudden death should only be used when the cause is of a cardiac origin as per standard definition (see guidance notes for completing the SAE reporting form [20]). The terms death and sudden death are clearly distinct and must not be used interchangeably.

The study will comply with all local regulatory requirements and adhere to the full requirements of the ICH Guideline for Clinical Safety Data Management, Definitions and Standards for Expedited Reporting, Topic E2 ([Appendix 2](#)).

7.1.2 Treatment and Follow-up of AEs

AEs, especially those for which the relationship to study medication(s) is not “unrelated”, should be followed up until they have returned to baseline status or stabilized. If after follow-up, return to baseline status or stabilization cannot be established an explanation should be recorded on the eCRF.

7.1.3 Laboratory Test Abnormalities

Laboratory test results will be recorded on the laboratory results eform of the eCRF, or appear on electronically produced laboratory reports submitted directly from the central laboratory, if applicable. Recommendations for grading adverse events and laboratories abnormalities can be found in [Appendix 4](#).

Any treatment-emergent abnormal laboratory result which is clinically significant, i.e., meeting one or more of the following conditions, should be recorded as a single diagnosis on the AE eform in the eCRF:

Accompanied by clinical symptoms

Leading to a change in study medication [e.g. dose modification, interruption or permanent discontinuation]

Requiring a change in concomitant therapy [e.g. addition of, interruption of, discontinuation of, or any other change in a concomitant medication, therapy or treatment].

Any laboratory result abnormality fulfilling the criteria for a serious adverse event [SAE] should be reported as such, in addition to being recorded as an AE in the eCRF.

7.1.3.1 Follow-up of Abnormal Laboratory Test Values

In the event of medically significant unexplained abnormal laboratory test values, the tests should be repeated and followed up until they have returned to the normal range and/or an adequate explanation of the abnormality is found. If a clear explanation is established it should be recorded on the eCRF.

7.2 Handling of Safety Parameters

7.2.1 Reporting of Serious Adverse Events [immediately reportable]

Any clinical AE or abnormal laboratory test value that is *serious* [as defined in Section 7.1.1.3 above] and which occurs during the course of the study, regardless of the treatment arm, must be reported to Roche within 24 hours of the investigator becoming

aware of the event [expedited reporting]. The investigator must complete the *SAE Reporting Form* and forward it to the SAE Responsible.

The investigator must fax the completed SAE reporting form directly to the Roche local country contact person for SAEs (local monitor, see the Administrative and Contact Information).

Related SAEs *MUST* be collected and reported regardless of the time elapsed from the last study drug administration, even if the study has been closed.

Unrelated SAEs must be collected and reported during the study and for up to 30 days after the last dose of study medication.

This study adheres to the definition and reporting requirements of ICH Guideline for Clinical Safety Data Management, Definitions and Standards for Expedited Reporting, Topic E2. Complete information can be found in [Appendix 2](#).

As an exception, the following SAEs unrelated to study drug, which are common in the dialysis population, will not be reported in an expedited manner on an SAE reporting form (but will be recorded as SAEs on the AE pages of the eCRF):

- Thrombosis of vascular access for dialysis in HD patients
- Peritonitis in PD patients

All SAEs, including the two categories listed above, occurring during the randomized treatment period or within 30 days after the last injection of MIRCERA® or other ESAs within study, should be documented as SAEs on the AE eforms of the eCRF (See Figure in [Appendix 1](#)).

7.2.2 Pregnancy

No data are available from adequate, controlled studies of MIRCERA® or other ESAs in pregnant women. Therefore, women of childbearing potential must have a serum pregnancy test at screening and must use a reliable method of contraception throughout the study (see [Appendix 3](#)).

A female subject must be instructed to stop taking the study medication and immediately inform the investigator if she becomes pregnant during the study. The investigator should report all pregnancies within one working day to the sponsor using the *Pregnancy Reporting Form*. The investigator should counsel the subject, discuss the risks of continuing with the pregnancy and the possible effects on the fetus. Monitoring of the patient should continue until conclusion of the pregnancy. Pregnancies occurring up to 90 days after the completion of the study medication must also be reported to the investigator.

7.3 Warnings and Precautions

No evidence available at the time of the approval of this study protocol indicated that special warnings or precautions were appropriate, other than those noted in the SmPC [[14](#)].

7.4 Loss of effect

Hb values will be monitored regularly throughout the study, and dose adjustments to achieve target Hb levels will be made according to protocol guidance (6.1).

Loss of effect is defined as: a decline in Hb of at least 2.8 g/dL in a 4-week period without transfusion *or* requirement for transfusion of one blood unit or more per week for a minimum of two consecutive weeks in the absence of overt bleeding or blood loss, under uninterrupted treatment with study drug and with dose changes according to protocol guidance [18].

If loss of effect is suspected, the cause should be actively sought. Possible causes include: iron deficiency, infection, inflammation, occult blood loss, hyperparathyroidism, myelofibrosis, and malignancy. If a cause for loss of effect is not found, a hematologist should be consulted (bone marrow examination) and an unscheduled blood sample should be obtained for a reticulocyte count and an anti-erythropoietin antibody determination.

If a diagnosis of PRCA is not confirmed, the patient should be maintained on the study drug and other possible causes of loss of effect should be investigated.

If a diagnosis of PRCA is confirmed, treatment with the study drug should be stopped. The patient should not receive another epoetin and causes of PRCA should be investigated. The patient should proceed with the study assessments as scheduled. In addition, reticulocyte counts and anti-erythropoietin antibody testing will be performed every 8 weeks until the end of the study (see [Appendix 5](#)).

8. STATISTICAL CONSIDERATIONS AND ANALYTICAL PLAN

8.1 Primary and Secondary Study Endpoints

8.1.1 Primary Endpoints

The primary efficacy endpoint for this study is the time to composite of:

- all-cause mortality
- non-fatal cardiovascular events (MI, stroke)

defined as the time between first dose of study medication and the date of death or non-fatal cardiovascular events (MI, stroke), whatever occurs first. Patients for whom no endpoint event is captured on the clinical database are censored at their last day in the study.

8.1.2 Secondary Endpoints

Secondary endpoints are the time to the individual components of the composite endpoint: the time to death, the time to non-fatal cardiovascular events (MI or stroke), the time to MI and the time to stroke.

8.1.3 Other Safety Endpoints

The safety of the treatment will also be evaluated on the basis of AEs, laboratory tests and vital signs, as described in section [8.2.6](#).

All subjects who receive at least one dose of treatment will be included in the safety evaluation.

8.2 Statistical and Analytical Methods

8.2.1 Statistical Model

8.2.1.1 Primary Endpoint

The analysis of time to event endpoints is based on the survivor function, which is the probability to survive or, more generally, to remain event-free beyond a certain point in time. The primary endpoint will be analyzed with a Cox's proportional hazards model to estimate the hazard ratio and its 95% confidence interval between the two treatment groups. The underlying proportional hazards model is $\lambda(t) = \lambda_0(t)\exp(\beta Z)$. Thereby, β is the coefficient corresponding to the binary vector Z taking the value 0 for patients on the reference arm and the value 1 for patients on the MIRCERA® arm, and $\lambda_0(t)$ is the baseline hazard of the reference treatment. Based on this, the following non-inferiority hypothesis for the hazard ratio ($h_{MR} = \exp(\beta)$) between MIRCERA® and reference will be tested by comparing the upper limit of the 95% confidence interval for the hazard ratio to 1.20:

$$H_0: h_{MR} \geq 1.20 \quad \text{versus} \quad H_1: h_{MR} < 1.20$$

The null hypothesis will be rejected if the upper limit of the confidence interval is below 1.20. The underlying Cox regression model will retain treatment as factor.

In addition, analyses based on Cox models adjusted for the baseline stratification factors and other clinically relevant baseline variables such as CRP at screening, age and baseline risk factors will be reported.

8.2.1.2 Secondary Endpoints

Kaplan-Meier methods and frequency tables will be used to describe the time to the composite endpoint as well as the time to the individual components of the composite endpoint for the MIRCERA® versus reference group. The survival function will be summarized for the 25th percentile, the median, the 75th percentile and their 95% confidence intervals. The plot of Kaplan-Meier estimates for the two treatment groups will be presented. The un-stratified log-rank test will be used to compare survivor functions between the two treatment groups.

In addition, analyses based on Cox models adjusted for the baseline stratification factors (including CRP) and other clinically relevant baseline variables such as age and baseline risk factors will be reported.

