The primary objective is to demonstrate non-inferiority of MIRCERA® versus reference ESAs in terms of a composite endpoint of all-cause mortality and non-fatal cardiovascular events (MI, stroke), based on a non-inferiority limit of 1.20 for the hazard-ratio of the composite endpoint and a one-sided significance level of 0.025. The model used for the non-inferiority analyses will be a Cox model on time to event with treatment as the independent variable but no co-variables included in the model. The analysis will be performed based on the safety population defined as all patients randomized who receive at least one dose and had at least one post-dose safety assessment.

Secondary analysis

In addition to the primary analysis, Kaplan-Meier methods and frequency tables will be used to describe the time to the composite endpoint as well as the time to the individual components of the composite endpoint for the MIRCERA® versus reference group.

Other analyses

The secondary objectives (incidence of anti-erythropoietin antibody-mediated PRCA, gastrointestinal bleeding and thromboembolic events), as well as hemoglobin over time and dose will be analysed using descriptive statistics and analytical methods such as risk ratios, Cox regression and ANOVA methods.

Demographic and baseline characteristics

Demographic and baseline characteristics (socio-demographic parameters, medical history and co-morbidities, co-medication, laboratory status and dialysis parameters, hemoglobin levels, duration and type of prior ESA treatments) will be summarized and comparability between treatment groups will be assessed descriptively.

Sample size

The stratification will be ensured that 20% of patients will be recruited in the correction setting and 80% in the maintenance switch setting. The expected yearly event rate is approximately 20%, based on

- an expected 25% composite endpoint rate (a mortality rate of approximately 16% [2, 3] and non-fatal cardiovascular morbidity of approximately 9% [4]) in the maintenance setting (80% of patients)
- a 7% rate for the combined endpoint in the correction setting (20% of patients) [CSR BA16738]

Assuming linear recruitment over 30 months and a follow-up time of 18 months after randomization of the last patient, a sample size of 2800 patients, representing approximately 7700 patient-years of exposure, would be adequate to observe 1264 events of the composite endpoint of death and non-fatal cardiovascular events.

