8.2.2 Sample Size

The randomization will be stratified by treatment setting (correction/maintenance) and baseline CRP category (≤ 30 mg/L / >30 mg/L). The stratification will ensure that 20% of patients will be recruited in the correction setting and 80% in the maintenance switch setting.

The expected yearly event rate is approximately 20%, based on

- an expected 25% composite endpoint rate (a mortality rate of approximately 16% [15, 16] and non-fatal cardiovascular morbidity of approximately 9% [17]) in the maintenance setting (80% of patients)
- a 7% rate for the combined endpoint in the correction setting (20% of patients) [CSR BA16738]

Assuming linear recruitment over 30 months and a follow-up time of 18 months after randomization of the last patient, a sample size of 2800 patients, representing approximately 7700 patient-years of exposure, would be adequate to observe 1264 events of the composite endpoint of death and non-fatal cardiovascular events.

1264 events are sufficient to ensure 90% power to establish non-inferiority of MIRCERA® to comparator ESAs in terms of the composite endpoint based on a non-inferiority margin of 1.20 and a one-sided significance level of 0.025.

Duration (months)	NI limit (HR)	Event rate per year	No. events / Nb patients	Expected Event rate at end of study (%)	Highest event rate based on NI limit (%)	Absolute / relative difference (%)	Absolute and relative difference in deaths (%)
48	1.2	0.2	1264 / 2800	45.2	51.2	6.1 / 13	3.6 / 13

Note: The overall event rate observed during the study is considerably lower than that expected at the planning stage. Changing no other parameters leads to an extended study duration; the occurrence of 1264 events has been estimated to be approximately 10 years after study start.

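### Non-fatal CV events, MI and stroke are described by Kaplan-Meier with no rule for deaths; if deaths are censored, 1 − KM overstates the probability of these events

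*Combined protocol and SAP*

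**What the plan says.** Section 8.1.2 lists time to death as a secondary endpoint, and with it "the time to non-fatal cardiovascular events (MI or stroke), the time to MI and the time to stroke". In Section 8.2.1.2, frequency tables and Kaplan-Meier estimation are "used to describe the time to the composite endpoint as well as the time to the individual components of the composite endpoint". It continues: "The survival function will be summarized for the 25th percentile, the median, the 75th percentile and their 95% confidence intervals", and "The plot of Kaplan-Meier estimates for the two treatment groups will be presented". An unstratified log-rank test and adjusted Cox models follow. The synopsis names only Kaplan-Meier methods and frequency tables for these endpoints.

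Section 8.2.1.1 interprets the survivor function as "the probability to survive or, more generally, to remain event-free beyond a certain point in time".

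The only censoring rule stands in Section 8.1.1, under the primary endpoint: "Patients for whom no endpoint event is captured on the clinical database are censored at their last day in the study". No section says what happens to a patient who dies without a prior MI or stroke when these components are analysed, and no competing-risk method is named. The plan also leaves open whether a fatal MI or stroke counts in the time to MI or the time to stroke.

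**The concern.** For the composite and for death, a death is an event and Kaplan-Meier is the right estimator. For non-fatal CV events, MI and stroke, a death ends the possibility of the event. Censoring it treats the patient as someone who could still have the event later. The curve then no longer has the meaning that Section 8.2.1.1 gives it, and 1 − KM is too high in each arm.

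Two steps here are readings of the text. The first is that the Section 8.1.1 rule carries over to the components. The second is that the percentiles and plot, written in the singular, apply to each component, which is the ordinary reading.

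Death is not a rare competing event in this population, and follow-up is now long. These are named secondary endpoints of a safety study, so readers are likely to take absolute risks from the component curves.

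**Working it through.** **Reproducing the plan's own figures.** With a margin of 1.20, one-sided 0.025, 90% power and 1:1 allocation, events = 4 × (1.960 + 1.282)² / (ln 1.20)² = 1264.4, against 1264 in Section 8.2.2. With 2800 patients, follow-up uniform over 1.5 to 4 years and an annual event probability of 20% (hazard −ln 0.8 = 0.2231), 45.2% have an event, which is 1264 patients. Both agree with the plan.

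**Rate used here.** Section 8.2.2 notes that "The overall event rate observed during the study is considerably lower than that expected at the planning stage" and puts event 1264 at about 10 years after study start. So I solved for the constant composite hazard h that gives 1264 first events among 2800 patients at 10 years, with uniform accrual over 2.5 years:

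- no loss to follow-up: h = 0.0688 per year
- assumed loss hazard 0.05 per year: h = 0.0895
- assumed loss hazard 0.10 per year: h = 0.1146

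**Split.** The documents give no observed split of first events. The main case takes 64% as deaths, from the planning ratio 16 : 9 in the maintenance setting (16/25 = 0.64). The range is 55% to 75%. With no loss, the death hazard is d = 0.64 × 0.0688 = 0.0440 and the non-fatal CV hazard is c = 0.36 × 0.0688 = 0.0248.

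**Formulas (constant hazards, deaths censored).**

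- 1 − KM tends to 1 − exp(−ct)
- Probability of the event (cumulative incidence): c/(c + d) × [1 − exp(−(c + d)t)]

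At 7.5 years, 1 − exp(−0.0248 × 7.5) = 16.9%, while 0.36 × [1 − exp(−0.0688 × 7.5)] = 14.5%.

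| Endpoint and case | Time (years) | 1 − KM | Cumulative incidence |
|---|---|---|---|
| Non-fatal CV, 64% deaths, no loss | 4 | 9.4% | 8.7% |
| same | 7.5 | 16.9% | 14.5% |
| same | 10 | 21.9% | 17.9% |
| Non-fatal CV, 55% deaths, no loss | 7.5 | 20.7% | 18.1% |
| Non-fatal CV, 75% deaths, no loss | 7.5 | 12.1% | 10.1% |
| Non-fatal CV, 64% deaths, loss 0.05 | 7.5 | 21.5% | 17.6% |
| Non-fatal CV, 64% deaths, loss 0.10 | 7.5 | 26.6% | 20.8% |
| MI or stroke at an assumed half of c, no loss | 4 | 4.8% | 4.4% |
| same | 7.5 | 8.9% | 7.6% |
| same | 10 | 11.6% | 9.5% |
| same, loss 0.10 | 7.5 | 14.3% | 11.1% |

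For comparison only, the superseded maintenance planning rates (16% death, 9% non-fatal CV per year; d = −ln 0.84 = 0.1744, c = −ln 0.91 = 0.0943) give 31.4% against 23.1% at 4 years.

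**Percentiles.** The KM 25th percentile is −ln(0.75)/c. For non-fatal CV events without loss it is 9.3, 11.6 or 16.7 years at 55%, 64% or 75% deaths. With 64% deaths it is 8.9 or 7.0 years at loss 0.05 or 0.10. For a half-rate component it is 23.2, 17.9 or 13.9 years at loss 0, 0.05 or 0.10, so it is not reached.

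**The case against.** The strongest reply is that nothing confirmatory rests on these curves. The non-inferiority test, the 1264 events, the power and the event-driven reviews by the monitoring board do not use them. The log-rank and Cox results for the components remain valid as cause-specific comparisons. All of this stands, and it caps the priority.

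The effect is also modest in the main case: 0.8 points at 4 years and 2.4 at 7.5 years for non-fatal CV events, and 0.4 and 1.3 for a half-rate component. Few patients will approach 10 years after a 30-month accrual. The percentiles will mostly not be reached. The 64% split comes from maintenance planning rates, and its 16% is total mortality, not death as a first event. These points stand as well, and they are why ranges are shown.

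The frequency tables are said to give an unbiased absolute summary already. That is true up to 7.5 years if nobody is lost. It fails when patients enter over 30 months and some leave early, for example at transplantation (Section 4.4), because a crude proportion then does not give the risk at a stated time.

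Finally, cumulative incidence has its own weakness: it depends on mortality. With equal non-fatal CV hazards and 1.2 times the death hazard in one arm, it reads 14.5% against 14.1% at 7.5 years (half-rate component 7.6% against 7.3%; planning rates at 4 years 23.1% against 21.8%), while KM is the same in both arms. So it should be added beside the hazard ratios and should not replace them.

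**Conclusion.** The concern holds. The plan names Kaplan-Meier for three endpoints that death can preclude and gives no rule for deaths. If they are censored, absolute risks read from those curves are too high in both arms. Without loss, the overstatement at 7.5 years is about 2.0 to 2.6 points for non-fatal CV events across death shares of 55% to 75%, or roughly 14% to 20% in relative terms. At an assumed loss hazard of 0.10 and 64% deaths it is about 5.9 points, or 28%.

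These figures rest on constant hazards, the rate implied by 1264 events at about 10 years, and assumed death shares, component shares and loss rates. For a single component they also assume that the death hazard is unchanged by the other component. The direction of the error needs only that deaths are censored and that some patients die without the event. The primary conclusion does not change. This is a cheap improvement of minor to moderate priority.

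**What to change.** In Section 8.2.1.2:

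- State for each component how deaths are handled, including whether a fatal MI or stroke counts as the component event or as the competing death.
- Add Aalen-Johansen cumulative incidence by arm for non-fatal CV events, MI and stroke, with death without that prior event as the competing event. Make it the source of absolute risks.
- Label any Kaplan-Meier plot or percentile kept for these three as censoring deaths, not to be read as absolute risk. Leave Kaplan-Meier unchanged for the composite and for death.
- Keep the log-rank and Cox analyses, label them cause-specific, and base the between-arm comparison on those hazard ratios, read beside the mortality hazard ratio.
- State that censoring at transplantation or other withdrawal (Section 4.4), and at the end of endpoint monitoring 30 days after the last dose (Section 5.4.1), is still assumed non-informative. Cumulative incidence does not remove bias from that source.

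The cost is a change of wording and standard software, with no new data. Because Section 8.2.1.2 is protocol text, changing it there goes through the modification procedure in Section 13. The statistical downside is the dependence on mortality shown above, which is why the curves are read with the mortality result.
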